⁶ To be performed at Week 8, 12, 16, 20, 24, 28, 32, 36, 40, 44, 48, 52, 56, 60, 64, 68, 72, 76, 80, 84, 88, 92, 96, 100, 104, 108, 112, 116, 120, 124, 128, 132, 136, 140, 144, 148, 152, 156, 160, 164, 168, 172, 176, 180, 184, 188, 192, 196, 200, 204, 208, 212, 216, 220, 224, 228, 232, 236, 240, 244, 248, 252, 256, 260, 264, 268, 272, 276, 280, 284, 288, 292, 296, 300, 304, 308, 312, 316, 320, 324, 328, 332, 336, 340, 344, 348, 352, 356, and 360 Visits (i.e., every 4 weeks).

⁷ If a facemask is used in Study 233AS101 or at screening and/or baseline of this study, it should be used for all SVC assessments for the duration of the study. If a facemask is not used during Study 233AS101 or at screening and/or baseline of this study, it should not be used for the duration of the study, if possible. If the participant begins the 233AS102 study not using a facemask but develops the need to use a facemask to complete the SVC during the study, then the facemask should be used for all subsequent SVC assessments for the duration of the study. Upright SVC will be determined by performing 3 to 5 measures. The results will be overread by a central reader to confirm that these criteria (at least 3 acceptable tests with the 2 highest acceptable [largest and next largest] efforts within 150 mL of vital capacity) have been achieved.

⁸ To be performed at Week 12, 24, 36, 48, 60, 72, 84, 96, 108, 120, 132, 144, 156, 168, 180, 192, 204, 216, 228, 240, 252, 264, 276, 288, 300, 312, 324, 336, 348, and 360 (i.e., every 12 weeks) Visits only.

[REDACTED]

[REDACTED]

CONFIDENTIAL

The information contained herein may not be used, disclosed, or published without the written consent of Biogen MA Inc.

¹²“Since Last Visit” version of C-SSRS will be used after the Baseline/First Loading Dosing Visit.

¹³ECGs to be done at Screening, Day 1, Final/Early Termination Visit, and as clinically necessary per the discretion of the Investigator throughout the study. ECGs will be obtained after participants have rested in a supine position for at least 10 minutes.

¹⁴A physical examination and limited neurological examination will be performed at the specified timepoints (Screening, Day 1, Final/Early Termination Visit). At all other visits, the physical and/or limited neurological examination may be performed at the Investigator’s discretion. The components of the limited neurological examination are coordination/cerebellar function, reflexes, and motor system.

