8.2. Exclusion Criteria

Candidates will be excluded from study entry if any of the following exclusion criteria exist at Screening, or at the timepoint specified in the individual criterion listed:

CONFIDENTIAL

The information contained herein may not be used, disclosed, or published without the written consent of Biogen MA Inc.

Medical History

1. History of drug abuse or alcoholism within 6 months before study enrollment that would limit participation in the study, as determined by the Investigator.
2. Presence of an untreated or inadequately treated active infection requiring systemic antiviral or antimicrobial therapy, or any other ongoing medical condition during the screening period that, according to the Investigator, would interfere with the conduct or assessments of the study.
3. Significant cognitive impairment, clinical dementia, or unstable psychiatric illness, including psychosis, suicidal ideation, suicide attempt, or untreated major depression ≤ 90 days, as determined by the Investigator.
4. History of allergies to a broad range of anesthetics.
5. Presence of risk for increased or uncontrolled bleeding and/or risk of bleeding that is not managed optimally and could place a participant at an increased risk for bleeding during or after an LP procedure. These risks could include, but are not limited to, anatomical factors at or near the LP site (e.g., vascular abnormalities, neoplasms, or other abnormalities) and underlying disorders of the coagulation cascade, platelet function, or platelet count (e.g., hemophilia, Von Willebrand's disease, liver disease).
6. Presence of an implanted shunt for the drainage of CSF or an implanted CNS catheter.
7. Clinically significant abnormalities in hematology or clinical chemistry parameters, as determined by the Investigator, which would render the participant unsuitable for enrollment.
8. Clinically significant, as determined by the Investigator, 12-lead ECG abnormalities, including corrected QT interval using Fridericia's correction method of > 450 ms for males and > 470 ms for females.

Medications

9. Prior or current treatment with small interfering RNA, stem cell therapy, or gene therapy.
10. Treatment with another investigational drug, biological agent (excluding BIIB067), or device within 1 month or 5 half-lives of study agent, whichever is longer.
11. Current or anticipated need, in the opinion of the Investigator, of a DPS during the study period.

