4.9.7. Columbia Suicide Severity Rating Scale (C-SSRS)

The details of derivation and imputation for C-SSRS is described in Appendix B. The following analyses on C-SSRS measurements will be conducted:

- Descriptive summary of subjects who answered “Yes” to any question 1-12 as well as subjects who had suicidal ideation or suicidal behavior at baseline and at any post-baseline visit. The denominator for baseline summary is the number of subjects who were dosed and had baseline assessment; the denominator for post-baseline summary is the number of subjects who were dosed and had at least one post-baseline assessment for each question.
- Descriptive summary of subjects who had treatment-emergent suicidal ideation, subjects who had new suicidal ideation as well as subjects who had worsening suicidal ideation. The denominator is the number of dosed subjects with both baseline and at least one post-baseline suicidal ideation assessment.
- Descriptive summary of subjects who had treatment-emergent suicidal behavior. The denominator is the number of subjects who answered “No” to all suicidal behavior questions at baseline and had at least one post-baseline suicidal behavior assessment.

Listing of subjects having treatment-emergent suicidal ideation will be provided. Subjects who had new suicidal ideation and subjects who had worsening suicidal ideation will be flagged. The listing will display both baseline and post-baseline Suicidal Ideation Scores for each subject. Listing of subjects having treatment-emergent suicidal behavior will also be provided.

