Appendix B: Derivation of C-SSRS

The Columbia Suicide Severity Rating Scale (C-SSRS) is an assessment that evaluates suicidal ideation and behavior. C-SSRS measurements are collected with respect to “Lifetime: time he/she felt most suicidal” at baseline, and with respect to “Since last visit” at last visit (Day 57 for Part A and Day 169 for Part B) and ET visit.

There are 11 common “Yes/No” questions at baseline and postbaseline visits. Five questions on suicidal ideation and five questions on suicidal behavior are re-ordered and follow increasing severity order respectively as shown in **Table 8**. In particular, only patients who answered “Yes” to question 2 will proceed to question 3, 4 and 5. Thus, for any subjects who answered “No” to question 2, an answer “No” will also be assumed to question 3, 4, and 5. An additional “Yes/No” question is used to record if subject had committed suicide in postbaseline visits.

Table 8: C-SSRS re-ordered questions

Suicidal Ideation	
Question 1	Wish to be dead
Question 2	Non-specific active suicidal thoughts
Question 3	Active suicidal ideation with any methods (not plan) without intent to act
Question 4	Active suicidal ideation with some intent to act, without specific plan
Question 5	Active suicidal ideation with specific plan and intent
Suicidal Behavior	
Question 6	Preparatory acts or behavior
Question 7	Aborted attempt
Question 8	Interrupted attempt
Question 9	Actual attempt
Question 10	Suicidal behavior
Question 11 (postbaseline visit only)	Suicide
Self-Injurious Behaviour without Suicidal Intent	
Question 12	Self-injurious behavior without suicidal intent

A subject is considered to have *suicidal ideation* at the period of interest if a “Yes” is answered to any of the five suicidal ideation questions (Question 1-5). A subject is considered to have *suicidal behavior* at the period of interest if a “Yes” is answered to any of the five suicidal behavior questions (Question 6-10) at baseline or a “Yes” is answered to any of the six suicidal behavior questions (Question 6-11) at postbaseline visit.

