A subject’s *Suicidal Ideation Score* is defined as the maximal suicidal ideation question number (maximal of 1-5) with an answer “Yes” per visit. The score is defined as 0 if the subject answered “No” to all 5 Suicidal Ideation questions at that visit. A subject is considered to have treatment-emergent suicidal ideation if the subject had either new or worsening suicidal ideation. A subject is considered to have new suicidal ideation if the subject’s Suicidal Ideation Score increased at postbaseline visit compared to a score 0 at baseline. A subject is considered to have worsening suicidal ideation if the subject’s Suicidal Ideation Score increased at postbaseline visit compared to a positive score at baseline.

A subject is considered to have treatment-emergent suicidal behavior if the subject answered “Yes” to any suicidal behavior questions at any postbaseline visit while answered “No” to all suicidal behavior questions at baseline.

Signature Page

Document Name: BIIB067_233AS102_SAP_Final_V4.0

Document Title:

Signed by	Role	Date / Time (UTC)
[REDACTED]	Signing as Approver	06-Aug-2024 06:26:08
[REDACTED]	Signing as Approver	05-Aug-2024 15:55:01
[REDACTED]	Signing as Approver	05-Aug-2024 16:49:09
[REDACTED]	Signing as Approver	05-Aug-2024 14:22:24

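### A lifetime-worst C-SSRS baseline means that repeat suicidal behaviour, and recurrent ideation no worse than before, is never classed or listed as treatment-emergent

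*SAP*

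**What the plan says.** **Recall periods.** SAP Appendix B states: "C-SSRS measurements are collected with respect to “Lifetime: time he/she felt most suicidal” at baseline". After that the recall is short. Protocol Section 4, footnote 12, reads: "Since Last Visit” version of C-SSRS will be used after the Baseline/First Loading Dosing Visit".

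**Behaviour.** Under Appendix B a subject has treatment-emergent behaviour on a Yes to any "suicidal behavior questions at any postbaseline visit while answered “No” to all suicidal behavior questions at baseline". SAP 4.9.7 restricts the table to match: "The denominator is the number of subjects who answered “No” to all suicidal behavior questions at baseline", with at least one post-baseline assessment also required. The listing follows the same definition: "Listing of subjects having treatment-emergent suicidal behavior will also be provided".

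**Ideation.** The visit score "is defined as the maximal suicidal ideation question number (maximal of 1-5) with an answer “Yes” per visit", or 0 if all five answers are No. Ideation is new if the score rises from 0. It is worsening if the "Suicidal Ideation Score increased at postbaseline visit compared to a positive score at baseline". The denominator is every dosed subject with a baseline and a post-baseline ideation assessment. The listing covers emergent subjects only.

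**Other outputs.** SAP 4.9.7 also counts subjects with a Yes to any of questions 1 to 12, and subjects with ideation or behaviour, at baseline and at any post-baseline visit, with no history filter. Protocol 16.6.2.4 promises a listing of C-SSRS data as well as descriptive summaries, and does not confine the listing to emergent cases.

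**Eligibility.** Protocol 8.2, criterion 3, concerns recent events: "suicidal ideation, suicide attempt, or untreated major depression ≤ 90 days, as determined by the Investigator". Older history does not exclude.

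**The concern.** The comparison sets a whole lifetime at its worst against an interval of about four weeks. A subject whose only attempt was years ago enters with a baseline Yes, although criterion 3 is meant to keep out people who are currently suicidal. A further attempt on treatment is new relative to that person's state at entry, yet the rule treats it as nothing new. The SAP's AE rule (4.9.1) works the other way: an event with onset on or after first dose is treatment-emergent whatever the past history.

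There is a second consequence for Part C subjects who had about six months of tofersen before entry (SAP Section 1). If the lifetime recall applies at entry to this study, suicidality that first arose on drug in 233AS101 becomes part of their baseline and can mask its own recurrence.

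At stake is whether a reader of the treatment-emergent C-SSRS table and listing can see recurrences on drug, in a study whose primary objective is long-term safety.

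**Working it through.** The plan gives no figure to reproduce, so the check is to run the Appendix B rules through every combination of baseline and on-study result.

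**Behaviour.** Emergent = post-baseline Yes and baseline all No.

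| Lifetime baseline | On study | Emergent | In emergent denominator | In emergent listing | In any-post-baseline summary |
|---|---|---|---|---|---|
| No | No | no | yes | no | no |
| No | Yes | yes | yes | yes | yes |
| Yes | No | no | no | no | no |
| Yes | Yes | no | no | no | yes |

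The last row holds for every behaviour item, including question 11, suicide. For a subject with past behaviour the rule returns the same answer whatever happens on study.

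**Ideation.** Let B be the baseline score (0 to 5) and P the highest post-baseline score (1 to 5). Emergent = P > B.

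| B | P flagged | P not flagged |
|---|---|---|
| 0 | 1, 2, 3, 4, 5 | none |
| 1 | 2, 3, 4, 5 | 1 |
| 2 | 3, 4, 5 | 1, 2 |
| 3 | 4, 5 | 1, 2, 3 |
| 4 | 5 | 1, 2, 3, 4 |
| 5 | none | 1, 2, 3, 4, 5 |

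For subjects with a history (B = 1 to 5) there are 5 × 5 = 25 cells with on-study ideation. Not flagged: 1 + 2 + 3 + 4 + 5 = 15. Flagged as worsening: 4 + 3 + 2 + 1 + 0 = 10. These are counts of rule cells, not probabilities. Only B = 5 is wholly blind. All these subjects stay in the ideation denominator, so an unflagged recurrence counts as a non-event.

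**Who could be affected.** The documents give no prevalence of lifetime behaviour. As an illustration only, take 2%, 5% or 10% of at most 183 subjects (the ceiling for dosing in 233AS101, hence an upper bound here). Then 183 × 0.02 = 3.7, 183 × 0.05 = 9.2 and 183 × 0.10 = 18.3, so about 4, 9 or 18 subjects would fall outside the behaviour table.

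**Listing.** Protocol 16.6.2.4 has C-SSRS data listed; SAP 4.9.7 lists emergent subjects only. SAP Section 5, which records departures from the protocol's analyses, names the efficacy and biomarker analyses and the enriched/other subgroups. It does not mention this narrowing.

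**Baseline source.** Appendix B names post-baseline visits at Day 57 for Part A and Day 169 for Part B. This study's schedule has C-SSRS at Day 1, Day 29, every four weeks from Week 8, and the final visit. SAP 2.2 says Day 197 of 233AS101 serves as baseline for most Part C subjects, and does not say which C-SSRS version was used then.

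**The case against.** **The events are counted elsewhere.** This is the strongest reply, and it stands. A repeat attempt appears under its own question in the any-post-baseline summary. If no baseline is missing, subtracting the emergent count from that summary's behaviour count even gives the number of subjects with recurrent behaviour. An attempt recorded as an AE or SAE, or a death, reaches the SAP 4.9.1 tables and listings regardless of history, and AE and SAE incidence is the primary endpoint. A reader might infer that on-study suicidality in these subjects would go unreported; the documents do not support that. What is missing is a C-SSRS output that says who they are and shows their history. A Yes on the scale need not have been entered as an AE.

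**The behaviour table uses an at-risk denominator.** SAP 4.9.2 does the same for laboratory shifts. This stands in part. Because history-positive subjects leave both numerator and denominator, one cannot call the behaviour proportion biased towards no signal without assuming that history raises risk, which the documents do not establish. But a laboratory value that is high at baseline describes the subject's state at entry; a lifetime answer does not.

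**Lifetime recall may not hold for everyone.** This also stands. The Appendix B visit wording does not fit this study, and Part C baselines may have used another version. It does not rescue the plan: emergent would then mean different things across the columns of SAP Table 6.

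**A tempting overreach.** A reader might take any lifetime history to make the rule blind. For ideation scores 1 to 4 it does not, since a higher on-study score is flagged and listed.

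**Conclusion.** The point holds in a limited form and is worth correcting. For behaviour the result is definitional: with any lifetime Yes, no on-study event can be emergent, enter that table or be listed as C-SSRS data. Ideation at lifetime score 5 is equally blind. At scores 1 to 4 the rule misses only recurrence at or below the lifetime worst.

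This rests on the lifetime baseline as Appendix B states it, and is uncertain for Part C subjects whose baseline comes from 233AS101. A percentage of events missed cannot be given: it would need the prevalence of history, the relative risk of recurrence and the share of scores above the lifetime worst, and the documents supply none of these. The primary endpoint is unaffected. The loss is in a supporting safety measure, together with an undeclared narrowing of the protocol's listing.

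**What to change.** Amend SAP 4.9.7 and Appendix B:

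1. List every subject with any post-baseline Yes, showing the baseline answers, with ideation and behaviour flagged new, worsening or recurrent as applicable. This also restores the listing in Protocol 16.6.2.4.
2. Add a row for recurrence on treatment, disjoint from worsening. For behaviour: any post-baseline Yes with a baseline Yes. For ideation: a post-baseline score of at least 1 that never exceeds a positive baseline score. The denominator is history-positive subjects with a post-baseline assessment. For ideation, new, worsening and recurrent then partition all subjects with on-study ideation and a known baseline (5 + 10 + 15 = 30 of the 6 × 5 = 30 cells), so nobody is counted twice.
3. Use baseline score 0 as the denominator for the new row and scores 1 to 4 for the worsening row. Removing only score 5 from the worsening row would leave in score-0 subjects, who cannot worsen by definition.
4. State the baseline recall period for each cohort, including Part C subjects whose baseline comes from 233AS101, and correct the Day 57/Day 169 wording.

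The cost is SAP wording, one extra table block and a longer listing, all from data already collected.
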